8.4.1.2 Allocation Concealment Mechanism

A masked computer algorithm will be used to generate the subset of patients for interview and deliver the outcome to researchers at the time that they are assigning patients to be invited to interview.

8.4.1.3 Implementation

A computer will generate the random allocation sequence and assign participants to interventions. Healthcare professionals at the pre-assessment clinics will enrol participants in the study.

8.4.2 Blinding

No blinding of participants will be done in the study, as all eligible patients will receive the same intervention. The clinicians listening to the call will be blinded to **DORA's** decisions when they are making their own assessments.

8.4.3 Methods of Data Collection

8.4.3.1 Quantitative data collection

The key data to be collected are **DORA** and the clinician's decisions. This will include data on symptoms as well as an overall assessment. Both **DORA** and the clinician will separately record their decisions about symptoms, clinical assessment, and management plan. **DORA** will record the decisions in the **DORA** database, which will be accessed by the study team during the evaluation to compare against the clinician decisions. Usability of the system will be assessed using the SUS and

TUQ questionnaires (see 13.4 Appendix 4). These will be delivered to all participants shortly after they have had the call with **DORA** via an online or paper survey (see Figure 6).

8.4.3.2 Qualitative data collection

A subset of participants will also be invited to an interview, so that more in-depth, qualitative feedback can be collected about the user experience with **DORA** (see Figure 6). For the interviews, a semi-structured interview approach will be followed (see 13.5 Appendix 5 for a sample topic guide). If patients consent, the interviews will be audio recorded and professionally transcribed. If not, the interviewer will take notes, and provide the notes to the patient at the end of the interview for verification.

Figure 6. Patient data collection flow diagram

8.5 Data Analysis

8.5.1 Statistical Methods for Primary Outcome

The primary analysis will be the calculation of a kappa statistic of inter-observer (**DORA** & clinician) reliability of the decision made. Additionally, the outcome of the assessment will be compared with the 'real' complication rate determined by hospital medical records. This will be established by identification of any hospital presentation within 90-days after the last call. Given the specialist nature of ophthalmology services it can be assumed that patients will present through the eye casualty or clinic services offered by each site. Patients who present to the hospital eye service will be analysed on a case-by-case basis to ensure that complications that were missed by **DORA's** original assessment and complications that developed later can be differentiated. This analysis will provide baseline sensitivity and specificity data for use in preparing subsequent evaluations of efficacy.

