5 STUDY SUMMARY

Table 3. Study Summary

| Table 3. Study Summary | |
|--------------------------|--|
| Study Title | A clinical investigation of an autonomous phone conversational agent for cataract surgery follow-up |
| Short title | Autonomous telephone follow-up after cataract surgery |
| Study Design | The study will be a multi-centre, mixed-methods clinical investigation to develop evidence regarding the feasibility, acceptability and potential effectiveness of DORA . |
| Study Participants | The study will include adults (aged 18 years or older) who are on the waiting list for either their first or second eye cataract surgery at Oxford or Imperial. To be eligible, the patients must have no history of significant ocular comorbidities and have a routine surgery with no intraoperative complications. |
| Planned Size of Sample | The planned sample size is 591 patients, split mostly equally between Oxford and Imperial clinical sites (see Table 1 for details on how this estimate was produced). |
| Follow up duration | Imperial: patients will receive the standard face-to-face appointment within a few days of having the autonomous call (dependent on current Covid-19 restrictions). |
| | Oxford: there will be no face-to-face follow-up for patients at the Oxford site as this is the standard of care. |
| | At both sites, an additional 3-month follow-up period where unplanned eye-related clinical visits will be recorded and assessed. |
| Planned Study Period | The total duration of the study will take up to 3 years, including the recruitment of patients, intervention refinement period, main intervention period, and analysis of results. |
| Research Question/Aim(s) | The aim of the study is to assess the evidence for the safety of using DORA to deliver autonomous cataract surgery follow-up assessments. This ability will be evaluated in comparison to an expert human clinician to assess the research question: Can DORA identify which patients need clinical follow up after a cataract operation? |

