8.2.4 Comparator(s)

Imperial sees all of their post-operative cataract patients at a face-to-face out-patient appointment with an ophthalmologist or specialist nurse. This is conducted between three to four weeks following the procedure. Therefore, patients at Imperial will receive their call from **DORA** within 3 days before their scheduled appointment (day 25-27 post-surgery). This will enable the results of the **DORA** call to be compared with the face-to-face appointment at Imperial to assess whether any complications were correctly identified and if the management plan remains the same.

For patients at both clinical sites, health records will be examined 90 days after the call to determine if the patient presented to an eye clinic with any complications from surgery. This comparison of the follow-up with actual complication rate will enable an assessment of **DORA's** safety (see Table 6).

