8.2.5.2 Secondary Outcomes

There will be several secondary outcome measures to assess the clinical safety, feasibility, usability, and acceptability of the system (see Table 6).

Clinical safety

To examine safety, two outcomes will be captured. Firstly, patients at both sites will have a retrospective case review of both general and ophthalmic electronic health records at 90 days after their initial operation. Complications will be identified from patient's medical records related to any unplanned eye-related clinical episode.

Secondly, all cataract surgery patients at Imperial were historically followed up face-to-face between 3-4 weeks post-surgery in a dedicated post-op clinic. Any complications requiring a change in patient management at slit lamp review or from attending eye casualty services (as the Oxford site does not normally perform face-to-face follow-ups) will be compared with the decisions made by **DORA** and the clinician. If Imperial changes their method of follow-up due to the COVID-19, assessment for complications will be done by checking hospital medical records as is done at the Oxford site.

Feasibility

Feasibility will be assessed by examining the proportion of autonomous calls that were completed without needing any intervention from the supervising clinician. All interruptions or clarifying questions of the supervised call will be logged; the supervising clinician will be asked to log the reason for asking clarifying questions. If clarifying questions were asked because the clinician felt that there was insufficient information for either individual symptoms or to make a management plan, the clinician's management plan before and after clarifying questions will be captured to see if clarifying questions changed the management plan.

Usability

Usability will be assessed using questions presented to patients following calls delivered by online and paper surveys distributed to participants. These questions will be drawn from the System

Usability Scale (SUS) and Telehealth Usability Questionnaire (TUQ; see 13.4 Appendix 4 for a sample survey) [14,15].

Acceptability, satisfaction, and appropriateness

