DORA's acceptability, satisfactoriness, and appropriateness will be assessed during qualitative interviews with a subset of the patients. These semi-structured interviews will provide an opportunity for patients to provide more in-depth feedback about what they liked about **DORA** and any barriers to use that they experienced during the call (see 13.5 Appendix 5 for a sample topic guide). The supervising clinician will also be asked to provide feedback about their level of satisfaction with the system and any safety concerns they might have.

Patients' willingness to recommend **DORA** to others will also be assessed at the end of the call [20]. **DORA** will calculate a net promoter score (NPS) by asking patients "on a scale of 1 to 10, how likely would you be to recommend this automated service to a friend or colleague." **DORA** will follow up by asking patients to "tell me why you gave that score."

Cost-effectiveness

Cost-effectiveness will be examined by collecting and analysing health economic data before and during the study. The costs of implementing **DORA** will be compared with historical data about the costs of the usual standard of care.

| Secondary Outcome | Outcome Measure | | | |
|-----------------------|---|--|--|--|
| Clinical Safety | Complications identified from patients' electronic health records up to 90 days following cataract surgery | | | |
| | Congruence between complications identified and management planned in DORA call and face-to-face follow up (Imperial) Comparison to data from patients attending eye casualty (Oxford) | | | |
| Feasibility | Proportion of autonomous calls that were completed without needing any intervention from the supervising clinician | | | |
| | Clinician-reported reasons for asking clarifying questions | | | |
| Usability | System Usability Scale (SUS) [14,17] | | | |
| | Telehealth Usability Questionnaire (TUQ) [15] | | | |
| | Qualitative feedback from semi-structured interviews | | | |
| Acceptability | Qualitative feedback from semi-structured interviews | | | |
| Satisfaction | Qualitative feedback from semi-structured interviews, Net Promoter Score (NPS) | | | |
| Appropriateness | Qualitative feedback from semi-structured interviews | | | |
| Cost-effectiveness | Comparison of the costs of implementing DORA and the costs of the usual standard of care | | | |
| Identify improvements | Synthesis of all of the outcome measures previously described | | | |

Table 6. Secondary Outcome Measurement

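### The 90-day record review has two start dates, and the SAP's safety tables have no step that carries in the protocol's missed-versus-later review

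*Protocol*

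**What the plan says.** **Start of the window.** Two places count from the call:
- 8.2.4: "health records will be examined 90 days after the call".
- 8.5.1: "identification of any hospital presentation within 90-days after the last call".

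Two places count from surgery:
- 8.2.5.2: "electronic health records at 90 days after their initial operation".
- Table 6: "electronic health records up to 90 days following cataract surgery".

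The study summary speaks of "an additional 3-month follow-up period where unplanned eye-related clinical visits will be recorded and assessed" and gives no start. Section 8.6 gives none either. The SAP names a three-month audit and a three-month flag, again without a start.

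**Missed versus later.** Section 8.5.1 requires patients who present to be examined one by one, so that complications missed by DORA's "original assessment and complications that developed later can be differentiated".

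**SAP tables.** Under clinical safety, the SAP builds the same 2x2 table three times. Each time it crosses `doraoutcomeupdate` with one 0/1 variable: `hospital-review-within-3-months`, `unexpected-change-management` or `unplanned-hospital-rev`. The first and third are coded simply as hospital review or no hospital review. No variable dates onset, and none marks a visit that the call itself set in motion.

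**Imperial's scheduled visit.** Section 8.2.4 places the Imperial call "within 3 days before their scheduled appointment (day 25-27 post-surgery"), so a planned hospital review follows almost at once.

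**The concern.** Objective 2 in 7.5 is to establish baseline sensitivity and specificity for detecting postoperative complications, and 8.5.1 passes these figures on to later evaluations. They answer that question only if the reference column holds complications that were there to be found when DORA made the call.

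Two things stand in the way. First, the same protocol gives two windows, so the set of countable events depends on which section the auditor follows. Second, the step that would turn hospital contacts into complications present at the call is required in the protocol and absent from the SAP. An analyst who follows the SAP literally would treat a contact as a complication, whenever it began and whatever prompted it.

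**Working it through.** **1. The two clocks (Imperial, call on day 25-27 by 8.2.4).**
- From the call: 25 + 90 = day 115 and 27 + 90 = day 117, so 90 post-call days.
- From the operation: the window closes on day 90, and 90 - 25 = 65 and 90 - 27 = 63 post-call days remain.
- The gap is 25-27 days. Post-call observation is 90/65 = 1.38 to 90/63 = 1.43 times longer on the call clock.
- Section 8.3.1.3 withdraws patients with unplanned review before the call. The pre-call days therefore add no unplanned events, and the operation clock really does shorten the useful window.
- The Oxford call day is not stated, so the same sum cannot be done there.

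**2. How the flags fill the table if used as written.**
- *Later onset.* A patient without a complication at the call whom DORA passed is a true negative. If a complication develops later and brings the patient in, the flag turns to 1 and the patient becomes a false negative.
- *Call-prompted visit.* Under 8.2.3, Stage 3, the patient is told the clinician's decision. A visit that follows from it can set `hospital-review-within-3-months` to 1 without any complication. It can also set `unplanned-hospital-rev` to 1 if such a visit is coded as unplanned, which the SAP does not say. The patient then counts as a true positive if DORA agreed with the clinician, or as a false negative if DORA had passed the patient. This is mainly an Oxford issue, because Imperial patients are seen anyway.

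**3. Scheduled Imperial visits, for `hospital-review-within-3-months` only.** Table 7's Imperial total reproduces:
- One-stop: 2 x 10 x (0.80 x 0.80 x 0.80 x 0.95 = 0.4864) x 0.70 x 26 x 0.85 = 150.5.
- Pre-assessment: 2 x 8 x (0.90 x 0.80 x 0.80 x 0.95 = 0.5472) x 0.70 x 26 x 0.85 = 135.4.
- Sum: 285.9, printed as 286.

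If the flag includes the scheduled visit, and attendance is as in the Appendix 6 audit (24/25):
- Coded 1: 286 x 24/25 = 274.6, about 275 patients, or 274.6/591 = 46% of the planned sample.
- Expected with a management change at that visit, at the audit's 7/25 = 28%: 286 x 0.28 = 80.1, about 80.
- Remainder coded 1 without one: 274.6 - 80.1 = 194.5, about 195.

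The audit prints 21% beside 7/25. That percentage equals 7/33, the number booked, so it is not used here. The 28% itself rests on 25 patients from one clinic type.

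**4. Late onset.** The documents give no usable rate. Among 30 operated patients, the Oxford audit (Appendix 7) reports one emergency attendance with CMO at week 10 (day 70). It also reports one telephone contact at week 6 (day 42) that needed no review. Onset is not given for either, and both fall inside either window.

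The effect per case can be shown only under assumptions. If *n* complications exist at the call and DORA detects all of them, one later-onset case in a passed patient takes sensitivity from 100% to *n*/(*n*+1). That is 10/11 = 91% for *n* = 10 and 20/21 = 95% for *n* = 20 (both *n* assumed), and 80/81 = 99% for *n* = 80 (step 3, Imperial only).

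**The case against.** The strongest reply has four parts.

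**The protocol already plans the separation.** Section 8.5.1 commits to it, and the SAP, a short variable list, does not say that the flags bypass the review. This stands as far as it goes. The gap is that the SAP does not put the review into operation, not that the sponsor overlooked the issue. An analyst working from the SAP alone still has nothing to apply.

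**Planned visits are partly handled.** A reader might infer that all three tables are swamped by scheduled Imperial appointments. The documents do not support that. `unplanned-hospital-rev` avoids the problem if it is coded as named, and 8.2.5.2 ties complications to unplanned episodes. The 275-patient figure concerns one table under one possible coding. It falls away if Imperial drops the face-to-face visit, as 8.2.5.2 allows.

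**Imperial has a near-simultaneous check.** A visit within 3 days of the call largely shows what was present at the call. Section 8.2.5.2 plans to compare "Any complications requiring a change in patient management at slit lamp review or from attending eye casualty services" with the decisions on the call. `unexpected-change-management` may be meant to carry this, but the SAP does not define it. The argument stands for Imperial while the visit is kept. It does not help Oxford, where patients are not routinely examined.

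**The wording about the last call.** A reader might take this as the last call of the whole study, which would give early patients a far longer window. Section 8.2.4 reads as a per-patient window, so that reading is strained. The phrase needs only a clearer wording.

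**Conclusion.** The point holds, as a change that should be made to a secondary safety analysis. The start-date conflict is plain on the text and amounts to 25-27 days at Imperial. The missing link between the review in 8.5.1 and the SAP tables is equally plain. Its consequences depend on the flags being used as written, which the SAP neither confirms nor excludes.

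Three stronger conclusions are not supported:
- *That the bias has a known direction or size.* Later onset, call-prompted visits and (for one flag) planned visits move patients into different cells, and no rates are available to net them.
- *That the clock is shown to reclassify real cases.* Both later Oxford audit contacts lie inside either window.
- *That the primary result is affected.* Section 8.5.1 stands under a primary-outcome heading, but the kappa compares DORA with the clinician and uses none of these flags.

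**What to change.** 1. Use one per-patient start date in the study summary, 8.2.4, 8.2.5.2, Table 6, 8.5.1, 8.6 and the SAP. The call date fits the question of what the call missed. In 8.5.1, refer to the patient's call.
2. Add one SAP field, coded in the review that 8.5.1 already plans: *present at call*, *later onset*, *indeterminate*, or *none (planned or call-prompted visit only)*. At Imperial, use the face-to-face findings to code it wherever that visit is kept.
3. Build the main safety 2x2 on *present at call* and list later-onset cases separately. Keep as sensitivity analyses the raw-flag tables and a table that counts *indeterminate* as a complication.
4. Exclude planned visits from `hospital-review-within-3-months`, or label that table as not being a measure of complications.
5. State that Oxford patients who pass and never present are unverified. The new field cannot repair this, so sensitivity there should be reported as an upper-end estimate.

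**Cost.** Wording in both documents and one coded field in a review already planned. Compared with the operation clock, the record check comes about four weeks later (25-27 days at Imperial). The raw-flag tables are kept, so no planned output is lost.

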7.2 Rationale

Like most operations, cataract surgery requires a post-operative check to monitor for complications and assess success. This has historically been performed with a face-to-face visit; prior to the Covid-19 pandemic, this was standard procedure for 72% of NHS Trusts [8]. However, this post-operative system has a high operational demand and is not always necessary; a recent ophthalmology Getting It Right First Time (GIRFT) report stated that a hospital review of cataract surgery patients is not required, if alternative follow-up arrangements are in place [8]. In the current context of the Covid-19 pandemic, face-to-face visits also pose a high risk for virus transmission due to the proximity of patient and clinician. This is reflected in the latest guidance from GIRFT and the Royal College of Ophthalmologists on restarting cataract surgery during the pandemic which recommends that patients should not be followed up in hospital after routine uncomplicated cataract surgery and should instead receive a telephone consultation or review with their local optometrist [9].

The solution developed to improve clinical efficiency for cataract surgery follow-up is a natural language, voice telemedicine conversation delivered to patients via telephone call (**DORA**, Ufonia). Since Ufonia's conception in 2016, several grants and partnerships have supported **DORA's** development and pilot testing at Buckinghamshire Healthcare NHS Trust (BHT), Department of Ophthalmology. For the patient, this is intended to be no different than a regular telemedicine consultation with a doctor or nurse; it does not require the download of an app, the provision of a device, or any training. This is important because the populations that consume the majority of healthcare services (elderly and socio-economically disadvantaged) tend to be relatively more digitally disenfranchised [10].

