8.6 Limitations

There are a couple limitations with the protocol. First, the number of issues identified during routine follow-up at the two sites cannot be directly compared. Unlike Imperial, Oxford does not proactively review patients following uncomplicated cataract surgery, instead relying on patients to self-present to the eye casualty service. This introduces a potential risk for missed complications if **DORA** decides

that a clinical review is not needed. However, this risk is minimised by the safety net established by the expert clinician oversight of the call and is a part of the current standard of care at the Oxford NHS Trust. The limitation is also mitigated by the examination of patient records after 90 days to identify any complications that might have been missed.

The second limitation is related to generalisability. The evaluation will only include patients who had uncomplicated cataract surgeries. This focus on routine care is important for establishing the feasibility of **DORA**, but means that **DORA**'s effectiveness for dealing with post-operative follow-up of complex patient groups cannot be assessed in this study. The National Ophthalmology Database (NOD) audit report however shows that the most common complication of posterior capsule rupture occurs in only 1-2% of patients [3].

Technical limitations of the system also affect generalisability. At present, patients with cognitive difficulties, hearing impairment or non-English speakers are not able to use **DORA** and will not be included in the study. However, this reflects the same limitations as human telemedicine services.

Finally, potential bias is introduced to the results by the use of qualitative interviews because of the influence of the interviewer on how participants respond (e.g. social desirability bias). This potential bias will be assessed by examining the balance of positive and negative feedback and by comparing the qualitative and quantitative data about **DORA's** usability.

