A Clinical Investigation of an Autonomous Phone Conversational Agent for Cataract Surgery Follow-up

NCT05213390

30 August 2022

Statistical analysis plan

Using the variables:

- doraoutcomeupdate (0 = pass, no review, 1 = fail, needs review)
- supervisoroutcomeupdate (0 = pass, no review, 1 = fail, needs review)

Primary outcome: Agreement between Dora and clinician for overall outcome decision and each symptom (x5)

- Inter-rater reliability (kappa)
- Accuracy (%)
- Data regarding true/false negatives/positives

	Clinician: follow-up (1)	Clinician: no follow-up (0)
Dora: follow-up (1)	ТР	FP
Dora: no follow-up (0)	FN	TN

• Sensitivity, specificity, AUC

Secondary outcomes

Clinical safety: Comparison with real complication rate

*Note: please do this analysis three times, once for each of the three complication measures
Data regarding true/false negatives/positives (Tables 2-3)

	Complications: 3 month audit	No complications: 3 month audit
Dora: follow-up	ТР	FP
Dora: no follow-up	FN	TN

- Sensitivity, specificity, AUC
- Variables
 - Dora follow up: "doraoutcomeupdate"
 - Complications:
 - "hospital-review-within-3-months"
 - 0 = no hospital review, 1 = hospital review
 - "unexpected-change-management"
 - 0 = no unexpected change management, 1 = unexpected change management

EUR ING [name] MA MSc MBA MPA PhD CEng FBCS Associate Professor of eHealth

"unplanned-hospital-rev"

• 0 = no hospital review, 1 = hospital review

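### The 90-day safety reference sees only complications that reach the study trusts, so misses treated elsewhere, mainly at Oxford, are counted as true negatives

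*Protocol*

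**What the plan says.** Protocol section 8.5.1 makes kappa between DORA and the clinician the primary analysis. It then compares DORA's assessment with a "complication rate determined by hospital medical records", established by "identification of any hospital presentation within 90-days after the last call". The reason given for trusting that source is the specialist nature of eye services, from which "it can be assumed that patients will present through the eye casualty or clinic services offered by each site".

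Section 8.2.5.2 describes the source as a "retrospective case review of both general and ophthalmic electronic health records at 90 days after their initial operation". For Oxford it is narrower: if Imperial stops its face-to-face visits, "assessment for complications will be done by checking hospital medical records as is done at the Oxford site".

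The SAP places this comparison under "Clinical safety: Comparison with real complication rate". It cross-tabulates DORA's decision with a three-month audit for three measures. Two of them code 0 as no hospital review; the third codes 0 as no unexpected change of management. The SAP does not split the tables by site.

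Section 8.6 acknowledges that Oxford depends on patients presenting themselves, and says the limitation is also "mitigated by the examination of patient records after 90 days to identify any complications that might have been missed". Section 7.2 reports national guidance that, after routine uncomplicated surgery, patients "should instead receive a telephone consultation or review with their local optometrist" in place of hospital follow-up.

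**The concern.** The reference standard is only as complete as the trusts' own records. A patient whom DORA passes, and whose complication is then handled by an optometrist, a GP or another hospital, has no hospital review and falls in the true-negative cell. Neither document plans to ask patients about such care or to obtain outside records. The case-by-case review in section 8.5.1 covers only patients who presented to the hospital eye service, so it cannot find the others. The same holds for the record review cited in section 8.6: it depends on the self-presentation whose failure it is meant to cover.

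The protocol's second objective is baseline sensitivity and specificity for detecting complications, and section 8.5.1 intends those figures for planning later evaluations. The false-negative cell matters most for safety, and it is the cell that loses cases.

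**Working it through.** **1. Who is exposed.** The documents give no capture rate, so there is no planned figure for it to reproduce. The site split comes from Table 7: patients per clinic × 2 screening days × eligibility × (0.70 consent × 26 weeks × 0.85 retained = 15.47).
- Imperial one-stop: 10 × 2 × 0.4864 × 15.47 = 150.5
- Imperial pre-assessment: 8 × 2 × 0.5472 × 15.47 = 135.4
- Oxford pre-assessment: 12 × 2 × 0.6156 × 15.47 = 228.6
- Oxford telephone: 4 × 2 × 0.6156 × 15.47 = 76.2

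The sites total 285.9 and 304.7 (printed 286 and 305), together 590.7 (printed 591). Oxford's share is 305/591 = 0.516.

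Section 8.2.4 has every Imperial patient seen face to face, with the DORA call within the 3 days before. A complication present at the call can therefore be found there whatever DORA decided. Imperial is exposed only for non-attenders, after that visit, or if COVID ends it (section 8.2.5.2).

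**2. Effect on the table.** Let S be true sensitivity, and let c1 and c0 be the shares of true complications that reach trust records among DORA-positive and DORA-negative patients.
- Recorded sensitivity = S·c1 / (S·c1 + (1 − S)·c0). This exceeds S only if c0 < c1.
- Recorded negative predictive value (NPV) = (TN + FN·(1 − c0)) / (TN + FN). This exceeds the true value whenever c0 < 1. The SAP does not list NPV, but it follows from its table.

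**3. Illustration for sensitivity (all inputs assumed).** Take 40 complications, 30 flagged and recorded and 10 missed, so S = 75%. Misses follow planned recruitment, so 10 × 305/591 = 5.16 are at Oxford. A fraction q of those goes elsewhere. Recorded sensitivity = 30 / (40 − 5.16q).

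| q | Misses lost | Recorded sensitivity |
|---|---|---|
| 0.2 | 1.03 | 30/38.97 = 77% |
| 0.5 | 2.58 | 30/37.42 = 80% |
| 0.8 | 4.13 | 30/35.87 = 84% |

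**4. Illustration for NPV at Oxford (assumed).** Take 305 patients, S = 0.80, specificity 0.90, c1 = 1, c0 = 0.50.
- Complication rate 10%: 30.5 complications, FN = 6.1, TN = 247.05. True NPV = 247.05/253.15 = 0.976; recorded = 250.10/253.15 = 0.988. About 3 misses move.
- Complication rate 28% (Imperial's audit count of 7/25, borrowed for Oxford): FN = 17.08, TN = 197.64. True NPV = 197.64/214.72 = 0.920; recorded = 206.18/214.72 = 0.960. About 8.5 misses move.

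**5. Equal capture.** With c1 = c0 = 0.50 at the 10% rate, recorded sensitivity stays at 12.2/15.25 = 0.80. NPV is still 0.988. Specificity falls from 0.90 to 250.1/289.75 = 0.863, because flagged patients treated elsewhere become false positives.

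**6. The audits.** At Imperial, where patients are actively reviewed, 7/25 = 28% (95% CI 12% to 49%) had a complication that changed management; Appendix 6 prints 21%, which matches 7/33 booked. At Oxford (Appendix 7), of 30 operated patients, 28 without surgical complications, 1 attended the emergency department and 1 telephoned: 1/28 to 2/28, or 3.6% to 7.1%.

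**The case against.** Several points on the other side are sound.

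- A reader might infer that section 7.2 contradicts section 8.5.1. It does not. The guidance offers a telephone consultation or optometrist review as alternatives, the DORA call is itself a telephone follow-up, and the text concerns routine follow-up rather than where a patient with a problem goes. It makes outside care plausible and no more.
- A reader might treat both sites as equally exposed. If all 10 misses in the illustration were exposed, recorded sensitivity would be 30/38 = 79%, 30/35 = 86% or 30/32 = 94%. That would require Imperial's visit to capture none of its misses, whereas the plan has every patient attend. Complications arising after that visit are to be separated case by case, where they are recorded, and need not be DORA misses.
- The direction of bias in sensitivity is not fixed. Section 8.2.3 has DORA convey the clinician's decision, so a patient DORA passes but the clinician flags is still told that review is needed. A patient DORA flags but the clinician passes may go elsewhere. Also, one SAP measure counts any hospital review within three months and is listed apart from unplanned reviews. If it includes planned reviews, it could add false negatives that are not complications.
- Section 8.5.1 puts its word for the complication rate in quotation marks, names the source and calls the results baseline data. Section 8.2.5.2 includes general as well as ophthalmic records, though their reach outside the trusts is not stated. Section 8.6 discloses Oxford's reliance on self-presentation and does not claim complete mitigation.

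These points narrow the size and location of the problem. They do not supply evidence for the capture assumption or any means of finding cases treated elsewhere.

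**Conclusion.** The point holds in limited form. The reference is complications recorded at the study trusts, not the real complication rate, and the gap lies mainly among the 305 planned Oxford patients. Considered alone, the leak overstates NPV whenever a passed complication is treated elsewhere. Sensitivity is overstated if capture is lower among DORA-negatives than DORA-positives. This is likely where patients told to attend enter the recorded pathway, but it is not certain. On the stated assumptions, a true 75% would read as about 77% to 84%; the documents give no figure to narrow that range.

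Two stronger conclusions are not supported. Sensitivity against this reference cannot be called an upper estimate in every case, for the reasons above. The gap between the two audits does not show that cases were treated elsewhere: the samples are small and not comparable, Oxford's follow-up was incomplete, and the gap would fit undiagnosed complications equally well. Those too would be scored as true negatives.

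The primary kappa analysis is unaffected. This is an inexpensive improvement to what the safety table can claim.

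**What to change.** 1. Delete the capture assumption in section 8.5.1. In sections 8.2.4 and 8.5.1 and the SAP, replace the real or actual complication rate by *complications recorded at the study trusts*. Do not add a statement that sensitivity is always an upper estimate.
2. Report the 2×2 tables by site, with the face-to-face finding as the reference at Imperial.
3. Add one day-90 question, through the existing online or paper channel, on care for the operated eye outside the trust. Ask the reason, so that a routine sight test is not counted.
4. Add a sensitivity analysis that counts patient-reported outside episodes as complications and varies the assumed capture among DORA-positives and DORA-negatives.
5. State in section 8.6 that the record review does not detect complications treated outside the trusts.
6. While editing, reconcile the window: sections 8.2.4 and 8.5.1 count 90 days from the call, section 8.2.5.2 and Table 6 from surgery.

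Cost: an amendment and one extra patient contact, since the present survey goes out shortly after the call. Response will be incomplete, self-reports will be unconfirmed, complications never diagnosed will remain unseen, and the safety figures may look less favourable.
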